Inclusion Criteria:	
Women must meet all inclusion criteria to participate:
 
 - Postmenopausal women with oestrogen-receptor positive non-metastatic breast cancer (TxMxM0) based on documented pathological and radiological evaluation - Ages 50-85 years (post-menopausal) 
Endocrine Therapy group:
 
 - Set to commence endocrine therapy as determined by the treating oncologist/commenced ET for no more than 8 weeks prior to recruitment 
OR
 
Control group:
 
 - Ductal carcinoma insitu (DCIS) – any grade not on ET/ Early stage, non-metastatic breast cancer not requiring ET - Treatment intended for at least 12 months - Eastern Cooperative Oncology Group (ECOG) 0 and 1 - Able to independently read and understand the participant information and consent form and provide written, signed and dated data informed consent to participate in the study - Able and willing to meet all protocol required procedures and visits
Exclusion Criteria:	
 - Cessation or switching ET during the 12 month study period

	
 - Previous hormone replacement therapy within 12 months of study recruitment - Glucocorticoid use (continuously for ≥ 2 weeks within the 6 months prior to screening) - Malignancy within the past 5 years including breast cancer requiring treatment (except non-melanoma skin cancers) - Established type 2 diabetes mellitus - Any disease which is likely to lead to serious illness or death within the study period - Self reported recreational drug use or alcohol dependence within 12 months of screening
Number of Planned Participants:	130
Statistical Methods:	
 • Longitudinal changes in the primary and secondary endpoints will be analyzed using paired-sample t-tests, generalised linear mixed models and generalised estimating equations and compared between patients with and without endocrine therapy • Adjustments will be made for age, comorbidities and baseline measurements
Subgroups:	
Tamoxifen Chemotherapy ER+ and HER2+ disease – commencing Herceptin as well as endocrine therapy Premature menopause/hysterectomy (<40yrs)

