3.2.4 Effects of Profound Oestradiol Deprivation on Mood and Behaviour

Studies reviewing psychological side effects are few and are conflicting in results. One uncontrolled study reviewed breast cancer survivors of whom 37 % were treated with hormonal therapy and reported one-third experienced a multifactorial psychological interference with their abilities to cope with their diagnosis, symptoms and treatment (24). Another study evaluated symptoms of depression in breast cancer patients treated with tamoxifen or exemestane and compared to healthy controls. Researchers indicated that there were no differences between patients and control groups with regard to mental health or depressive symptoms (25). Our study aims to assess the changes in mood and behavior in women on AI therapy when compared to a diagnostically comparable breast control group. While use of a control group of untreated women with breast cancer is not feasible, using women with a diagnosis of DCIS or early stage breast cancer not requiring ET, removes to some extent the important confounder of a recent cancer diagnosis.

Furthermore, although E2 deprivation has been reported in preclinical studies to directly impact on multiple somatic tissues including adipocytes to alter body composition and glucose metabolism, central nervous mechanisms that may lead to decreased energy levels or increased food intake either directly or secondary to behavioural effects of mood remains unclear in profound E2 deplete women. E2 is involved in the regulation of appetite and energy expenditure, and its elimination in rodent studies resulted in increased food intake and decreased ambulatory and wheel running activities, which was reversed with estrogen replacement (26, 27).

Physical Activity Frequency and Quality of Life assessment tools will shed light on the impact of profound E2 deprivation on the lifestyle, mood and exercise frequency of postmenopausal women on endocrine therapy and the potential indirect role it plays on body composition and therefore metabolic factors and cardiovascular health. If an association is observed, it would provide a basis for future targeted interventional studies to address and mitigate this mood and behavioural risks associated with endocrine and particularly AI therapy.

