3.3 NOVELTY AND CLINICAL SIGNIFICANCE

Our study will be a 24-month prospective, controlled, observational study investigating the biological effects of endocrine therapy, in particular, the profound oestradiol deprivation from endocrine therapy on body composition in oestrogen receptor positive, postmenopausal women. Controls will include aged-matched postmenopausal women with breast ductal carcinoma in-situ. The current mechanisms of how endocrine therapy, particularly aromatase inhibitors may affect cardiovascular risk remains unknown.

We hypothesize that endocrine therapy and its effects on oestradiol deficiency will lead to an increase in VAT, SAT and total body fat, along with other unfavourable changes on biomarkers of metabolic health including glucose metabolism, lipid profile, degree of liver steatosis, peripheral microvascular endothelial dysfunction and increased abdominal aortic calcification.

With cardiovascular disease being the highest cause for mortality in postmenopausal breast cancer survivors, having an easily accessible means of quantifying and measuring cardiovascular risk that can then be incorporated into the routine monitoring for these high-risk women is essential.

If deleterious changes in body composition and along with biomarkers of cardiovascular burden are observed with endocrine therapy, measures of these indirect biomarkers can be used to personalise endocrine therapy. By measuring these biomarkers, clinicians will be better able to stratify each patient's cardiovascular risk. Women identified as "high cardiovascular risk" can be managed pre-emptively for modifiable risk factors and the risk versus benefits of commencement and duration of endocrine therapy – particularly AI therapy, can therefore be individualised.

Furthermore, if an association between endocrine therapy and metabolic health is observed, this project will provide a basis for future targeted interventional studies to address and mitigate these biological changes that are indirect markers of cardiovascular risk.

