5.4 INCLUSION AND EXCLUSION CRITERIA

*INCLUSION CRITERIA

Women must meet all inclusion criteria in order to participate in the study.

- Postmenopausal women with oestrogen-receptor-positive, non-metastatic breast cancer (TxNxM0) based on documented pathological and radiological evaluation

- Age 50-85 years
- To commence adjuvant treatment with endocrine therapy as determined by treating oncologist/commenced endocrine therapy for no more than 8 weeks prior to recruitment
- OR
- Postmenopausal women with DCIS (any grade)/early breast cancer not requiring ET
- Endocrine therapy intended for at least 12 months
- ECOG 0 and 1
- Able to personally read and understand the Participant Information and Consent Form and provide written, signed and dated informed consent to participate in the study
- Able and willing to meet all protocol-required procedures and visits

Perimenopausal: absent cycles for 3-12months

Postmenopausal: absent cycles for 12 months

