***EXCLUSION CRITERIA**

Current evidence or prior history of any of the following:

- Malignancy within the past 5 years including breast cancer requiring previous treatment (not including non-melanoma skin cancer)
- Cessation or switch of endocrine therapy during the first 12 months
- Previous hormone replacement therapy within 12 months of study recruitment
- Established type 2 diabetes mellitus
- Self reported recreational drug use or alcohol dependence within 12 months prior to screening
- Any disease which is likely to lead to serious illness or death within the study period

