6. STUDY METHODOLOGY

6.1 STUDY VISITS

The following is a list of study interactions/visits and the data that will be collected. For the data collected please see section '6.3' for the specific measurements and techniques used.

- (i) **Screening of potential participants who consent:**
 - Medical interview and review of Austin Health medical file: demographic data (name, age, date of birth, hospital unit record number), and medical history and medication history sufficient to determine trial eligibility
 - For eligible participants, screening blood test and DXA scan will be used as baseline measurements if obtained within 8 weeks prior to entry into the trial
 - Patients are eligible for a baseline assessment if they plan to commence ET within 8 weeks of the assessment
- (ii) **Visit 1: Further baseline assessment of participants who are eligible based on screening**
 - Bloods tests
 - Medical Assessment and Anthropometric data
 - Questionnaires
 - DXA scan – measurements for bone mineral density/trabecular bone score, body composition and aortic calcification will be undertaken
 - EndoPAT peripheral arterial tonometry
 - Fibroscan
- (iii) **Visit 2: 6 months post recruitment**
 - Blood tests
 - Medical Assessment and Anthropometric data

- Questionnaires
- DXA
- EndoPAT peripheral arterial tonometry
- +/- Fibroscan (only if trends in liver function tests to suggest worsening steatosis or fibrosis)

(iv) **Visit 3: 12 months post recruitment**

- Blood test
- Medical Assessments and Anthropometric data
- Questionnaires
- DXA
- EndoPAT peripheral arterial tonometry
- Fibroscan

(v) **Visit 4: 24 months post recruitment**

- Blood test
- Medical Assessments and Anthropometric data
- Questionnaires
- DXA
- EndoPAT peripheral arterial tonometry
- Fibroscan

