8. STATISTICAL METHODS

8.1 STATISTICAL METHODS TO BE UNDERTAKEN

Longitudinal changes in the primary and secondary endpoints will be analyzed using paired-sample t-tests, generalised linear mixed models and generalised estimating equations and compared between patients with and without AI therapy. Adjustments will be made for age, comorbidities and baseline measurements.

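### Entry of ET women is tied to ET start, but controls have no time anchor, so the criteria do not ensure that the two groups are equally recent in diagnosis and treatment

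*Protocol*

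**What the plan says.** **ET women.** Protocol section 5.4 (and the Synopsis) takes women about to start ET, or who have "commenced endocrine therapy for no more than 8 weeks prior to recruitment". Section 6.1 adds: "Patients are eligible for a baseline assessment if they plan to commence ET within 8 weeks of the assessment".

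**Controls.** Section 5.4 asks for "Postmenopausal women with DCIS (any grade)/early breast cancer not requiring ET". The Synopsis wording for DCIS and early cancer is "any grade not on ET/ Early stage, non-metastatic breast cancer not requiring ET". Neither mentions a date of diagnosis, surgery or radiotherapy.

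**Why this control group.** The section on mood and behaviour (the second one numbered 3.2.4) says that using such women "removes to some extent the important confounder of a recent cancer diagnosis".

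**Handling of differences between groups.** Section 3.3: "Controls will include aged-matched postmenopausal women with breast ductal carcinoma in-situ". Section 8.1: "Adjustments will be made for age, comorbidities and baseline measurements".

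**Other rule on cancer timing.** Section 5.4 excludes "Malignancy within the past 5 years including breast cancer requiring previous treatment (not including non-melanoma skin cancer".

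**The concern.** The study is not randomised, so the AI-versus-control contrast is only as good as the comparability of the groups. The endpoints are 12-month changes. Mood, activity and weight may all move in the period after a cancer diagnosis and its local treatment. If AI women are mostly in that period and many controls are long past it, the difference in change contains time since diagnosis as well as the drug effect.

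The direction depends on the endpoint. Recovery of mood and activity in the AI group could hide harm. Weight gain after diagnosis could be read as an effect of the AI. Adjusting for the baseline value deals with different starting levels. It does not deal with women being at different points of a course that changes over time.

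This belongs in the protocol. A SAP can add a covariate, but it cannot set an entry window once recruitment has run.

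**Working it through.** The plan gives no figure on this point, so the check is mainly of the text.

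1. **ET clock.** Women who have started: ET start to recruitment is at most 8 weeks (5.4). Women who have not: assessment to planned ET start is at most 8 weeks (6.1). Entry therefore falls from 8 weeks before to 8 weeks after ET start, a band of 8 + 8 = 16 weeks. The anchor is ET start. It bounds time since diagnosis only indirectly, and the Synopsis lists a chemotherapy subgroup in whom ET may start well after diagnosis.
2. **Control clock.** None in the Synopsis, 5.4 or 6.1. Section 6.1 does require screening bloods and DXA used as baseline to be no more than 8 weeks old at entry. That dates the measurement, not the disease.
3. **Recruitment source.** Section 5.3 names a clinic for women commenced on ET, plus referrals. It does not say that controls come from newly diagnosed cases.
4. **Five-year malignancy exclusion.** Read literally, it bars the index cancer of every ET woman. Read workably, it concerns cancer before the current episode. On either reading it does not require the index disease to be recent, and its application to DCIS is unclear.
5. **Matching and adjustment.** Age; then age, comorbidities and baseline values. Time since diagnosis or treatment is in neither list.

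**Form of the bias.** Let d be the 12-month change due to the early course after diagnosis and treatment, and let f_C and f_AI be the shares of controls and AI women already past that course. Then

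expected difference = AI effect + [(1 − f_AI) − (1 − f_C)] × d = AI effect + (f_C − f_AI) × d.

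The documents give none of f_C, f_AI or d. The bias is zero if f_C = f_AI, and its sign reverses if the AI women are the later group.

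**Illustration only, all inputs assumed.** With f_C − f_AI from 0.25 to 0.75 and d from 0.2 to 0.5 SD:
- low: 0.25 × 0.2 = 0.05 SD
- high: 0.75 × 0.5 = 0.375 SD

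For scale, 40 per group at 80% power and two-sided 0.05 (section 5.2) corresponds to (1.96 + 0.84) × √(2/40) = 2.80 × 0.2236 = 0.63 SD. If both are on the same SD scale, which the protocol does not establish, the illustration runs from 0.05/0.63 = 8% to 0.375/0.63 = 60% of that difference. This shows only that the bias could be trivial or material.

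**The case against.** The strongest reply has four parts.

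- **The protocol claims little.** It says the confounder is removed only in part. A reader might infer that the control arm fails to remove it. The documents do not support that: controls still share a DCIS or breast cancer diagnosis, and many may be recent in practice. What stands is that the criteria do not ensure it.
- **ET women have no diagnosis window either.** A reader might take the 8-week rules to place ET women soon after diagnosis or surgery. They run from ET start, and ET can come late after chemotherapy. This narrows the contrast between the groups, but it also means that recency is uncontrolled on both sides.
- **The rationale concerns mood and behaviour, which are secondary endpoints.** A reader might infer that the primary visceral fat result is shown to be biased. No statement or figure in the protocol says so. The extension is plausible on the protocol's own reasoning: the same section gives mood and exercise a possible indirect role in body composition, and section 3.2.2 faults earlier work for prior chemotherapy because of its effects on intake and activity.
- **Other rules may help.** The five-year exclusion could keep out some controls with invasive cancer treated years ago, and section 5.3 speaks of women under treatment at the site. Neither is a window, and long-past DCIS is the case least clearly covered.

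The covariate list may also be expanded in a SAP that is not shown. That answers the adjustment part, not eligibility.

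**Conclusion.** The point holds as a gap in eligibility that should be closed. Entry of ET women is anchored to a treatment start, entry of controls is anchored to nothing, and neither age matching nor the listed adjustments compensate. The control group may therefore not deliver even the partial control of recent diagnosis that the protocol gives as its purpose for mood and behaviour. For body composition the same problem is plausible but unquantified.

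No size can be derived from the documents. The 0.05 to 0.375 SD range rests wholly on assumed inputs and should not be cited as an estimate. The conclusion rests on two assumptions: that 12-month change depends on time since diagnosis or treatment, and that controls enrolled under the text would differ from AI women in that time.

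**What to change.** **Preferred.** In the Synopsis and section 5.4, state one maximum interval from diagnosis or last local treatment (surgery or radiotherapy) to baseline, applying to both groups. The protocol has no such interval for ET women now, so it must be chosen for both and not borrowed from one.

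**If that would slow control recruitment too much.** Record the dates of diagnosis, last local treatment and any chemotherapy for all women. Frequency-match controls to AI women on the interval so that the groups overlap, and add it to the adjustment set in section 8.1. The history taken at screening under 6.1 is only what eligibility requires, so these dates should be named as data items, including for women referred from private practice.

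**In either case.** State that the five-year malignancy exclusion refers to cancer before the index episode, and how it applies to DCIS.

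**Cost.** An eligibility line, or a few extracted dates and one covariate. A window or matching may exclude some long-past controls and slow recruitment towards the 50 planned. A covariate alone excludes nobody, but it is weak if the groups overlap poorly, because the adjustment then rests on extrapolation.

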***EXCLUSION CRITERIA**

Current evidence or prior history of any of the following:

- Malignancy within the past 5 years including breast cancer requiring previous treatment (not including non-melanoma skin cancer)
- Cessation or switch of endocrine therapy during the first 12 months
- Previous hormone replacement therapy within 12 months of study recruitment
- Established type 2 diabetes mellitus
- Self reported recreational drug use or alcohol dependence within 12 months prior to screening
- Any disease which is likely to lead to serious illness or death within the study period

5.5 CONSENT

Prior to study entry which includes screening for eligibility, participants who wish to take part in the trial will have a detailed verbal discussion with a study doctor regarding all details of their participation in the trial. This will involve details about the imaging studies to be undertaking, blood collection procedures, storage, analysis (including potential future genetic testing), and publication of results. All this information will be available in writing via the Participant Information Consent Form (PICF). Participants will be able to take this form home and discuss with their relatives/friends/local health worker if they wish prior to deciding whether or not to take part in the study. They will be allowed to ask questions regarding any information in the PICF. After this, the participant is willing to take part in the

study, the participant will sign the Consent Form in the PICF to acknowledge that they have given informed consent. No part of the study will be undertaken until the participant signs the PICF. The participant will be given a copy of the PICF to keep for their records.

Individual informed consent will be obtained from each participant prior to any part of the study being undertaken. Participants will be provided with a copy of the signed Participant Information Consent Form. It will be explicit from the verbal and written consent process and throughout the study, the participation is voluntary, and that withdrawal is allowed. It will also be made very clear that their treatment in the clinic and their relationship with their doctors will not be affected by participation or non-participation.

6. STUDY METHODOLOGY

6.1 STUDY VISITS

The following is a list of study interactions/visits and the data that will be collected. For the data collected please see section '6.3' for the specific measurements and techniques used.

- (i) **Screening of potential participants who consent:**
 - Medical interview and review of Austin Health medical file: demographic data (name, age, date of birth, hospital unit record number), and medical history and medication history sufficient to determine trial eligibility
 - For eligible participants, screening blood test and DXA scan will be used as baseline measurements if obtained within 8 weeks prior to entry into the trial
 - Patients are eligible for a baseline assessment if they plan to commence ET within 8 weeks of the assessment
- (ii) **Visit 1: Further baseline assessment of participants who are eligible based on screening**
 - Bloods tests
 - Medical Assessment and Anthropometric data
 - Questionnaires
 - DXA scan – measurements for bone mineral density/trabecular bone score, body composition and aortic calcification will be undertaken
 - EndoPAT peripheral arterial tonometry
 - Fibroscan
- (iii) **Visit 2: 6 months post recruitment**
 - Blood tests
 - Medical Assessment and Anthropometric data

- Questionnaires
- DXA
- EndoPAT peripheral arterial tonometry
- +/- Fibroscan (only if trends in liver function tests to suggest worsening steatosis or fibrosis)

(iv) **Visit 3: 12 months post recruitment**

- Blood test
- Medical Assessments and Anthropometric data
- Questionnaires
- DXA
- EndoPAT peripheral arterial tonometry
- Fibroscan

(v) **Visit 4: 24 months post recruitment**

- Blood test
- Medical Assessments and Anthropometric data
- Questionnaires
- DXA
- EndoPAT peripheral arterial tonometry
- Fibroscan

6.2 STUDY SCHEDULE

Visit month	Event	Time (hrs)	Assessments	Standard Care	Dosage/Volume (blank where N/A)
Informed consent					
0	Screening visit	1	Medical interview	X	
0	Baseline Assessment	3	Medical assessment and Anthropometric data (1hr)	X	
			Blood tests (30min)	X	22.5ml standard care 20ml additional for study
			DXA** (30-45min) (whole body composition, trabecular bone score and abdominal aortic calcification)	X	0.06mSv
			EndoPAT (15 min)		
			Fibroscan (10min)		
			Questionnaires (10min)	X	

3	No visit	0	Blood tests	X	22.5ml standard care 20ml additional for study
6	Study visit 6 months from baseline	3	Medical assessment and Anthropometric data	X	
			EndoPAT		
			+/- Fibroscan		
			Questionnaires	X	
			Blood tests	X	22.5ml standard care 20ml additional for study
			DXA**		0.06 mSv
12	Study visit 12 months from baseline	3	Medical assessment and Anthropometric data	X	
			EndoPAT		
			Fibroscan		
			Questionnaires	X	
			Blood tests	X	22.5ml standard care 20ml additional for study
			DXA**	X	0.06 mSv
24	Study visit 24 months from baseline	3	Medical assessment and Anthropometric data	X	
			EndoPAT		
			Fibroscan		
			Questionnaires	X	
			Blood tests	X	22.5ml standard care 20ml additional for study
			DXA**	X	0.06 mSv

* Assessment without an 'X' are in addition to standard care

** Assessment of total body composition and abdominal aortic calcification are in addition to standard care, which involves scanning of the hip and spine

6.3 TESTS, MEASUREMENTS AND TECHNIQUES

6.3.1 Body composition by DXA

Visceral adipose tissue, subcutaneous adipose tissue, total body fat and lean body mass will be studied by DXA (Hologic with Apex 5.6 software). Bone mineral density and trabecular bone scores will also be measured as part of standard care.

